3. STUDY DESIGN

The EMMED-HF trial will be a single blinded (to patient), randomized, parallel group, active controlled, single center experimental design. 52 subjects with HFpEF and DM2 will comorbidities will be recruited to participate (N = 26 ertugliflozin group, N = 26 placebo group) with a 12 week study intervention period.

Enrollment/Randomization procedure

Subjects will be screened by qualified practitioners for eligibility to participate in the EMMED-HF clinical study. Once the subject has been determined to be eligible, an enrollment visit will be scheduled. Those subjects that meet the inclusion criteria and do not possess any exclusion criteria will be deemed eligible for enrollment by key study personnel and then undergo randomization to treatment arm. Randomization into treatment group will occur at baseline at a 1:1 ratio.

Primary endpoint

The primary endpoint is to assess the degree of change in peak exercise oxygen uptake (peak VO2, ml/kg/min) as measured by metabolic gas exchange during a MRIcardiopulmonary exercise test (CPET-ExMR) protocol.

Secondary endpoints

Change in LV mass index (gm/m2) measured by MRI imaging will be a pre-specified secondary endpoint. An additional pre-specified secondary endpoint will be fasting serum β -hydroxybutyrate (ketone body).

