7.2 Statistical analysis

The results of experiments will be analyzed by several statistical methods. Continuous variables will be analysis as the group mean and standard deviation. Categorical variables will be analyzed with a χ^2 test between groups. Continuous variables will be analyzed with t test for normally distributed variables and Wilcoxon 2 sample test for skewed distribution continuous variables. ANOVA will be used for evaluation of multiple continuous variables between groups. Curve fitting functions will be used for the detection of associations, using standard software (e.g., Graph pad prism 5.0). In all cases, p<0.05 will be considered as statistical significance.

Sample Size and Power Calculations: Our power analysis is based on physiologic outcome measures of primary and secondary endpoints estimated from the reported literature on heart failure with preserved ejection fraction. Power calculations were performed in R software.

For the primary endpoint, peak exercise oxygen uptake (VO2 peak), increased VO2 peak is a marker for reduced mortality and morbidity with associated increase in cardiopulmonary fitness in heart failure with preserved ejection fraction patients.25, 26 The primary endpoint for this trial is increase in VO2 over the duration of the study period. Baseline peak VO2 exercise performance in HFpEF has been reliably reported at 11.7 ml/kg/min in the RELAX trial26 with a within-patient standard deviation for peak VO2 in HFpEF of 2.0 ml/kg/min (used for both INDIE-HFpEF and RELAX trials).25,26 To calculate the primary endpoint power, the ss.1way function with variables: (k=2, alpha=0.05, beta=.2, f=.4, B=100) was used. For a power of 80%, assuming 5% type I error and a standard deviation of 2.0 ml/kg/min, we must enroll 26 subjects to detect a 2.0 ml/kg/min change from baseline in peak VO2 difference between the mean of placebo and ertugliflozin groups based on power calculation.

A secondary endpoint of left ventricular mass by CMRI (measured concurrently to VO2 during Ex-CMR protocol) will be measured. Reduced left ventricular (LV) mass is a marker of response to heart failure therapy. A reduction of LV mass by 10 gm has been reported as a significant marker of clinical response.24 (The same group reported a standard deviation of 9.6 gm for a 10 gm mean change in LV

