mass in heart failure patients.30 For a power of 80% assuming 5% type I error, we must enroll 20 subjects to detect a 10 gm change in LV mass assuming a standard deviation of 9.6 gm.

A secondary endpoint of change in fasting serum β -hydroxybutyrate (μ mol/L) will be measured. Ferrannini et al. report fasting BHB levels of 246 (standard deviation 288) prior to exposure to empagliflozin21 with an increase to 561 after 4-week exposure to drug. For a power of 80%, assuming 5% type I error, we must enroll 18 subjects to detect a 125% increase in fasting serum β hydroxybutyrate.

	Parameter	Reference	δ (Change)	SD (ơ)	N (90% power)
Primary Endpoint:					
Oxygen uptake	VO ₂ (ml/kg//min)	25, 26	2.0	2.0	21
Secondary Endpoints					
Ventricular Mass (measured by CMRI)	MRI measured LV Mass (gm)	24	5	4	14

21

125

117

18

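### Fasting beta-hydroxybutyrate is planned as a mean/SD summary with an unadjusted t test or Wilcoxon test chosen by an unstated skewness rule; its scale, summary and baseline adjustment should be fixed in advance

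*Combined protocol and SAP*

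**What the plan says.** Section 3 makes this a named endpoint: "An additional pre-specified secondary endpoint will be fasting serum" beta-hydroxybutyrate. Section 7.2 governs its analysis only through general rules. The summary rule is "Continuous variables will be analysis as the group mean and standard deviation". The test rule is "t test for normally distributed variables and Wilcoxon 2 sample test for skewed distribution continuous variables". The threshold is "In all cases, p<0.05 will be considered as statistical significance".

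No test is assigned to beta-hydroxybutyrate. The section gives no criterion for skewness and no transformation. It names no baseline-adjusted model for this endpoint, and no effect estimate or confidence interval. It does not say whether the test is run on week-12 values or on change, although the sample-size text describes the endpoint as a change in µmol/L.

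The planning figures are "fasting BHB levels of 246 (standard deviation 288) prior to exposure", then "with an increase to 561 after 4-week exposure to drug", and the conclusion is that "we must enroll 18 subjects to detect a 125% increase in fasting serum" beta-hydroxybutyrate. The assay is scheduled at Visit #2 and Visit #3 (schedule table in Section 4.3; Serum Chemistries & Metabolomics in Section 4.4), so a baseline value will exist.

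**The concern.** The plan's own mean and SD rule out anything close to a normal distribution, yet the prescribed summary is the mean and SD. The choice of test is left to a judgement with no stated criterion or timing. That choice matters: under the models below, the two permitted tests on change differ by about 8 to 13 percentage points of power at correlation 0.5, and which one is better depends on the shape of the data. A Wilcoxon p-value alone would also leave Aim 2 without an estimate of effect size. Finally, a baseline measurement that could sharpen the comparison at no cost is not used as a covariate.

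**Working it through.** **Inputs.** From Section 7.2: baseline mean 246, SD 288, post-treatment mean 561, significance level 0.05. From Section 3: 26 per arm. Assumed because the documents do not say: two-sided testing, no dropout, distributional shape, and a log-scale correlation between baseline and week 12 of 0.3, 0.5 or 0.7.

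**1. The plan's sample size.** With an additive effect, δ/SD = (561 − 246)/288 = 315/288 = 1.094. By the normal approximation, n per arm = 2(1.960 + 1.282)²/1.094² ≈ 17.6, so 18 at 90% power. At 80% power, 2(1.960 + 0.842)²/1.094² ≈ 13.1, so 14. The stated 18 is therefore reproduced per arm at the 90% of the table heading, not at the 80% of the text. The table's 125 and 117 look like the same figures as a percentage of baseline (288/246 = 117%); that row is broken in the available text, so this is a reading.

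**2. Skewness.** Mean minus one SD = 246 − 288 = −42. A normal distribution would put Φ(−246/288) ≈ 20% of values below zero. A lognormal with these moments has log-SD √ln(1 + (288/246)²) = 0.93, median about 160 and skewness about 5.

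**3. Power if lognormal with a multiplicative effect.** Simulated at ratio 2.25 (the 125% increase) and 26 per arm. Ranges are the spread over repeated simulations.

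| Analysis | corr. 0.3 | corr. 0.5 | corr. 0.7 |
|---|---|---|---|
| t test on raw change | 64% | 75% | 88% |
| Wilcoxon on change | 75–77% | 86–88% | 97% |
| Wilcoxon on week-12 values | 85% | 85% | 86% |
| Log ANCOVA | 89–90% | 94–95% | 99% |

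Against the better of the two Wilcoxon options, log ANCOVA gains about 4–5 points at 0.3 (89–90 against 85), 7–8 at 0.5 (94–95 against 86–88) and 2 at 0.7 (99 against 97). At correlation 0.5 and smaller ratios, Wilcoxon on change against log ANCOVA is 53–55% against 68% (ratio 1.75) and 32% against 43% (ratio 1.5). Type I error was 4–5% for all methods.

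**4. Source of the gain.** At ratio 561/246 = 2.28 and without a covariate, the log t test and the Wilcoxon test are nearly equal. On week-12 values they have 88% and 86%. On change they have 76/88/98% and 77/88/98% at the three correlations. The log alone is worth about −1 to +2 points. ANCOVA on ranks, with no log, reaches 92–93% at ratio 2.25 and correlation 0.5, close to log ANCOVA. Baseline adjustment does most of the work.

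**5. Sensitivity to shape.** A gamma distribution with the same mean and SD has shape (246/288)² = 0.73, so values pile up near zero: about 10% lie below 13 µmol/L and 5% below 5. At ratio 2.25 and correlation 0.5, power is 70–71% for the raw-change t test, 62–63% for Wilcoxon on change, about 62% for rank ANCOVA and 52–54% for log ANCOVA. With an assumed floor of 25 µmol/L, log ANCOVA recovers to about 62–64%, level with Wilcoxon but still below the t test.

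**The case against.** The strongest reply is that the plan already deals with skew: Section 7.2 sends skewed variables to the Wilcoxon test, and on the plan's figures beta-hydroxybutyrate belongs there. On week-12 values that test is unaffected by a log transform. At ratio 2.25 and correlation 0.5 it has 86–88% power on change in the lognormal case, above the 80% quoted in the text. This stands. A reader might infer that the plan is tied to an inefficient raw-scale t test, or that a log analysis is clearly more powerful. The documents support neither: the t test is only one of two options, and one mean and SD show skewness but not lognormality.

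A reader might also infer that the planned effect is a constant ratio. The text does speak of a percentage increase, but it also defines the endpoint as a change in µmol/L, and its sample size follows from an additive formula. A multiplicative effect is an assumption of the calculation above. Nor can the point be extended to the other assays, because the documents give no distributional figures for them.

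Nothing in the plan prevents reporting medians or a Hodges–Lehmann estimate, and judging skewness before unblinding would limit the harm from a late choice. But the plan commits to neither. Its silence on summary, scale, estimate and covariate is what remains.

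**Conclusion.** The point holds as one of pre-specification and efficiency for a secondary endpoint. Mean and SD summarise this variable poorly, the choice between the two tests has no rule, and the Visit #2 value is collected but not used as a covariate. These follow from the text and from 246 (SD 288) alone.

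The size of the benefit is conditional. With roughly lognormal data and a multiplicative effect at ratio 2.25, moving from Wilcoxon on change to log ANCOVA raises power by about 12, 7 and 2 points at correlations 0.3, 0.5 and 0.7 (89 − 77, 95 − 88, 99 − 97), mainly through baseline adjustment. With a gamma shape at correlation 0.5 it costs about 11 points (63 − 52), and roughly nothing if low values are floored at 25 µmol/L. Confidence is high that the analysis is under-specified and only moderate that the log scale is the most powerful choice.

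**What to change.** Add to Section 7.2 a short paragraph for this endpoint, before unblinding:

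- Main analysis: natural log of the week-12 value regressed on arm and natural log of the Visit #2 value, reported as a ratio of geometric means with 95% CI. Name Visit #2 as the covariate, because the Visit #1 laboratory list in Section 4.4 also includes this assay.
- A fixed substitution for values below the assay limit, since near-zero values drive the loss in the gamma case.
- Summary by median (IQR) or geometric mean.
- The Wilcoxon test or a rank ANCOVA as a sensitivity analysis.
- A statement that the target is a ratio. If a difference in µmol/L is wanted instead, say so and keep the baseline covariate.

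The cost is a few sentences and no new data. The downside to record is the possible loss of power if many values lie near zero; the rank-based sensitivity analysis gives a check on this.

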8. DATA COLLECTION AND QUALITY ASSURANCE

Fasting serum β-hydroxybutyrate (µmol/L)

8.1 Data Collection Forms

Serum ketone

bodies

The research coordinator will perform primary data collection based on sourcedocumented hospital and clinic chart reviews. For source documentation regulations require that Investigators maintain information in the study Subject's medical records that corroborate data collected on the CRFs. In order to comply with these regulatory requirements, at a minimum, the following information should be maintained:

• Sufficient medical history/physical condition of the study Subject before involvement in the study to verify protocol entry criteria (if not already present);

- Dated and signed notes on the day of entry into the study including clinical site number, assigned Subject number, and a statement that consent was obtained;
- Document consent process and verify original signed consent by monitor;
- Dated and signed notes from each study Subject visit with reference to the CRFs for further information, if appropriate (for specific results of procedures and exams);
- Notations on abnormal lab results;
- Adverse events reported, results of diagnostic tests ordered, treatment given, clinical outcome, and their resolution;
- Dictated procedure report;
- Dictated summary;
- Notes regarding concomitant medications taken during the study;
- Study Subject's condition upon completion of, or withdrawal from, the study.

8.2 Data Management

Data management will be overseen by the primary investigator, [name], will assign roles to the research staff for collating and conducting off-line analyses of the recorded clinical parameters. A study

database will be established in the University Hospital REDCap system for secure data storage and will be accessible only to qualified study personnel. Data contained in the REDCap database will be deidentified with use of only the subject number. The primary investigator, [name] and the study coordinator will be the only members of the study team that have access to the master subject list with identifying subject information.

8.3 Quality Assurance

Arrangements for data and procedural reviews by a quality assurance monitor will made in collaboration with the UH Center for Clinical Research and Technology. The study sponsor, Merck Co. will also make arrangements to review the study binders and provide additional quality assurance.

9.12 Institutional Review Board

It is the Primary Investigator's responsibility to submit the clinical protocol and any Amendments to the IRB/EC, if required, for approval prior to any Subject being enrolled at that Investigational Site and to obtain renewals at periods determined by the IRB/EC for the duration of the study.

